1.2.1 Descriptive Analysis

Location, age group, sex, self-reported race and ethnicity, occupation, preexisting medical conditions, SARS-CoV-2 vaccine history during prior seasons (as feasible), and frequency of mask-use while in close proximity of others during the SARS-CoV-2 circulation period will be summarized overall and by vaccine group. All demographics and baseline characteristics will use the mITT population.

6.1.2 VE Primary Objective

The primary analysis for VE will be a superiority test comparing vaccine efficacy (VE) between participants who receive either the NVX 2023-2024 updated vaccine (Arm 1) or Pfizer mRNA 2023-2024 updated vaccine(Arm 2) with the non-vaccinated participants who are recommended to be vaccinated based on CDC, state or organizational guidelines but decline the 2023-2024 updated vaccine. Cox proportional hazards models will use the Andersen and Gill counting method⁴² with participants able to contribute time at risk for each day of follow-up. Cox proportional hazard models will have randomized vaccine group versus the non-randomized arm as the main effect. For both primary objectives age, prior COVID-19 vaccination in the past 4 years and week will be adjusted for (time-varying covariate). Prior COVID-19 vaccination will be categorized (Never vaccinated, 1 prior vaccine (2 course vaccination), 2 prior vaccines (initial vaccination and 1 additional vaccine dose), 3 prior vaccines and ≥4 prior vaccines), if there are less than 30 people in a category, then we will collapse down (e.g. ≥3 instead of 3 and ≥4) until we have stable estimates. Other baseline characteristics will be included as covariates if there are significant imbalances between vaccine groups and kept in the model if they adjust the hazard ratio by ≥5. If an analysis has <10 events, an unadjusted model only will be calculated.

If models for a single month do not meet the proportional hazard assumption, the Andersen and Gill counting method will be used to allow for weekly circulation as a covariate. If a model still does not meet the assumption the proportional hazards assumption after the inclusion of weekly circulation as a covariate, the Prentice, Williams, and Peterson total time model⁴³ will be used with season as a strata

and circulation as a covariate, allowing for circulation to vary. Participants who do not experience an SARS-CoV-2 case prior to the discontinuation of the study will be right censored at their last response to weekly surveillance contacts.

6.1.3 Relative VE Primary Objective

The primary analysis for relative VE efficacy against SARS-CoV-2 illness for NVX (2023-2024 formula) vaccinated participants versus Pfizer mRNA (2023-2024 formula) vaccinated participants will be calculated using time at risk with the following null and alternative hypotheses for the objective comparing NVX vs mRNA:

 H_0 : rVE < -50 and H_a : rVE \geq -50

Here rVE is estimated with the same analytic approach described for the VE, however the Cox proportional hazard models will have NVX vaccinated arm versus the mRNA vaccinated arm as the main effect. The primary objective will be achieved if the lower limit of the one-sided confidence interval of rVE estimate exceeds -50 between NVX and mRNA vaccine groups, adjusting for potential confounders or differences in baseline groups.

6.1.4 Secondary Objectives

Incidence of SARS-CoV-2 will be calculated using Poisson regression with vaccine group as a main effect, and study month as covariates and log person weeks as an offset. Person weeks is defined as the time at risk (in days) divided by seven and rounded up. If assumptions for Poisson regression do not hold, zero-inflated Poisson and Negative Binomial models will be considered instead.

Proportional hazard or logistic regression analyses will be used to assess hazard ratio or relative risk and associated 95% confidence intervals for secondary endpoints such as individual, occupational, and environmental predictors of SARS-CoV-2 infection and of asymptomatic infection versus symptomatic COVID-19 illness. The choice to use PH or logistic model will depend on the specific secondary outcome being identified. If PH models are used, time-varying covariates will be used as available. Multivariable models will be adjusted for potential confounders.

7. Data Entry and Management

Westat will host and maintain a permission-based research data platform and study database for this trial. University of Utah study staff will have access to the database. Tracking databases with participant identifying information and contact information will be kept securely according to the standard operating procedures with respect to cybersecurity, privacy, participant confidentiality, and compliance with applicable HIPAA regulations. Any study-related papers with personal identifiers will be stored in a locked cabinet or other secure, limited-access area in the research offices of University of Utah.

All survey data will be entered directly into the study database through the use of online surveys, the text messaging interface, and/or the mobile application. Study site staff will enter response data directly

into the database if surveys are administered by telephone or in person interviews. The questions in the approved forms will appear on the research data platform rather than in paper form.

All study related documents and samples will contain a unique identifier per person. The online, mobile application, text message, and data entry screens will provide some Quality Assurance and Quality Control (QA/QC) thorough the use of logic and range checks and automated skip patterns. Additional quality checks of the data will be performed on a weekly basis including checks for out-of-range values and missing data.

Rapid antigen test results will be entered directly into the study database by the participant or study staff.

Upon execution of an appropriate data use agreement (DUA), data extracted from the state registry will be loaded into the database following the specifications of the study codebook and data dictionary (to be developed and submitted as an amendment to the IRB prior to implementation).

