Novavax's (NVX-CoV2373) protein based, novel but traditional immunizations have potential scientific advantages to the population through enhanced cross-reactivity which may facilitate activity against Coronavirus disease 2019 (COVID-19) variants.^{1,2} This technology also provides significant safety assurances to those wishing to utilize traditional immunization technology for their vaccination.³ There are two main challenges thought to largely explain the development of COVID-19 breakthrough infections: combination of variant mutations in the spike protein along with declines in antibodies.⁴

This randomized controlled trial (RCT) is comparing recipients of the 2023-2024 updated COVID-19 vaccines vs. non-recipients and Novavax (NVX) vs. mRNA 2023-2024 updated vaccines. The primary study hypothesis is to compare vaccine efficacy (VE) between participants who receive a 2023-2024 updated vaccine (mRNA or NVX) and participants who are recommended by the Advisory Committee on Immunization Practices (ACIP) to be vaccinated but decline the updated vaccine. The secondary hypothesis is to determine the relative vaccine efficacy (rVE) of the mRNA and the NVX 2023-2024 updated vaccines in preventing SARS-CoV-2 infection to confirm non-inferiority for NVX. This RCT may show evidence of the superiority of a blended vaccination approach of combining vaccines with different platforms.⁵

The trial will be conducted at the University of Utah (UT) Health for the upcoming SARS-CoV-2 virus circulation from Fall of 2023 to Spring of 2024. We aim to enroll 1500 participants who previously received at least two doses of the mRNA COVID-19 vaccine at least 90 days prior to enrollment. Upon enrollment, participants will be asked to describe their intention to receive a COVID-19 2023-2024 updated vaccines or not. Those who decide not to receive a vaccine during the study period will be placed in a non-randomized comparison group (n=300). Participants who intend to get vaccinated (n=1200) will be randomized into the NVX vaccine group or the mRNA vaccine group. Eligible participants will be randomized 1:1 to receive 1-dose of the NVX vaccine versus mRNA vaccine during November 2023 through February 2024. All eligible participants will be stratified by their age and sex within the respective groups.

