4.2 Secondary Objectives

- 1. Evaluate the effect of prior number of doses of COVID-19 vaccination during the preceding 3 years on the relative efficacy of a single dose of NVX.
- 2. Assess the vaccine efficacy against asymptomatic or any (asymptomatic or symptomatic) RAT-confirmed SARS-CoV-2 infections.
- 3. Examine the individual, occupational, and environmental predictors of SARS-CoV-2 infection and compare these predictors between asymptomatic infection versus symptomatic COVID-19 illness.
- Describe the clinical characteristics and outcomes associated with COVID-19.³⁷
 - a. Determine the duration and severity of illness and examine the socio-demographic and health characteristics associated with prolonged or severe illness.
 - b. Determine the impact of COVID-19 on indicators of functioning, including missed work, ability to complete normal work and home activities, and working while ill.
 - c. Determine the proportion of COVID-19 illnesses that are medically attended and examine the factors associated with seeking medical care and treatment.
- 5. Compare illness characteristics and duration with primary vs. re-infection with SARS-CoV-2 during the study window.
- 6. Examine if VE is modified by socio-demographic characteristics, occupation, health status, or other risk factors.
- 7. Examine if 2023-2024 formula (monovalent, Omicron XBB.1.5 containing) vaccines modifies illness severity and duration among participants with breakthrough infection despite vaccination.
- 8. Assess the incidence of post-COVID conditions (PCC) and factors associated with PCC symptoms.
- Determine if PCC symptoms differ among vaccinated and participants who decline the 2023-2024 updated vaccine.
- 10. Determine if PCC symptoms are modified by vaccination status (e.g. 2-, 3-, and 4+ doses) prior to infection.
- 11. Characterize the knowledge, attitudes, and practices (KAPs) of participants related to new COVID-19 2023 vaccine variant vaccines and examine the associations between KAP and subsequent vaccination behaviors (including vaccine refusal, hesitancy, or incomplete adherence to vaccination recommendations).

5. Methods

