# 7. GENERAL ISSUES FOR STATISTICAL ANALYSIS

# 7.1 Adjustment for Covariates

Cox proportional hazard models will have vaccine group as the main effect. For the primary objectives age, prior COVID-19 vaccination in the preceding 3 years and week will be adjusted for (time-varying covariate). Prior COVID-19 vaccination will be categorized (1 prior vaccine (2 course vaccination), 2 prior vaccines (initial vaccination and 1 booster), 3 prior vaccines and  $\geq$ 4 prior vaccines), if there are less than 30 people in a category, then we will collapse down (e.g.  $\geq$ 3 instead of 3 and  $\geq$ 4) until we have stable estimates.

Other baseline characteristics will be included as covariates if there are significant imbalances between vaccine groups and kept in the model if they adjust the hazard ratio by  $\geq 5\%$ . If there is evidence that the proportional hazard assumption is not met, weekly SARS-CoV-2 circulation will be added as a covariate or will be investigated for stratifying the baseline hazard. Covariates will not be used in subgroup models, where they are the event of interest. Season will not be included in models of SARS-CoV-2 type and subtype if they only occur in one season. If an analysis has <10 events, an unadjusted model only will be calculated.

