#### **8.3.2** Secondary Objective Analyses

Incidence of SARS-CoV-2 will be calculated using Poisson regression with vaccine group as a main effect, and study month as covariates and log person weeks as an offset. Person weeks is defined as the time at risk (in days) divided by seven and rounded up. If assumptions for Poisson regression do not hold, zero-inflated Poisson and Negative Binomial models will be considered instead.

Proportional hazard or logistic regression analyses will be used to assess hazard ratio or relative risk and associated 95% confidence intervals for secondary endpoints such as individual, occupational, and environmental predictors of SARS-CoV-2 infection and of asymptomatic infection versus symptomatic COVID-19 illness. The choice to use PH or logistic model will depend on the specific secondary outcome being identified. If PH models are used, time-varying covariates will be used as available. Multivariable models will be adjusted for potential confounders.

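### The Poisson incidence model adjusts for study month only, so its rate ratios against self-selected decliners are open to confounding by prior doses

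*Protocol*

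**What the plan says.** Protocol 6.1.4 gives one model for incidence: "Incidence of SARS-CoV-2 will be calculated using Poisson regression with vaccine group as a main effect, and study month as covariates". SAP 8.3.2 has the same model: "Poisson regression with vaccine group as a main effect, and study month as covariates and log person weeks as an offset". Neither names an age or prior-dose term. SAP 8.1 lists Poisson regression as the method for comparing event rates.

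The paragraph that follows in both sections covers proportional hazards and logistic models for other secondary endpoints. It ends: "Multivariable models will be adjusted for potential confounders". No covariates are listed there.

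The primary Cox model is specified more fully. SAP 7.1 says: "For the primary objectives age, prior COVID-19 vaccination in the preceding 3 years and week will be adjusted for". Protocol 6.1.2 and SAP 8.3.1 fix the same three terms, although they count prior vaccination over 4 years instead of 3. Further covariates are conditional: "Other baseline characteristics will be included as covariates if there are significant imbalances between vaccine groups", and they stay only if they move the hazard ratio.

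The decliners (n=300) are a non-randomized comparison group (Protocol, opening summary). Table 1 in Protocol 5.4.1 sets age-by-sex recruitment goals for both groups. It sets none for prior doses.

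**The concern.** The contrast between vaccinees and decliners is observational within this trial. The plan recognises this in the primary Cox model by fixing age and prior-dose category as covariates. The Poisson model carries vaccine group as a main effect and could produce the same contrast, but it adjusts only for study month.

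The plan gives some reason to expect different dose histories. Protocol 6.1.1 expects decliners to include people who are fully vaccinated but not boosted. It also derives its two planning rates (60 and 48 per 100,000 person-days) from last season's fully vaccinated and bivalent-boosted people, so it links dose history to infection rate.

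At stake is how incidence rate ratios are read beside the primary VE. If one is adjusted for prior doses and the other is not, a gap between them may reflect the adjustment and not a difference in protection.

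**Working it through.** **The plan's own figure.** None is stated for the Poisson model. The VE sizing in Protocol 6.1.1 was reproduced to confirm the inputs.
- Event probability in decliners: 60/100,000 × 168 days = 0.1008, which is a hazard of -ln(1 - 0.1008) = 0.10625.
- Events for VE 56.25%: (1.960 + 0.842)² / (0.2 × 0.8 × ln(0.4375)²) = about 72.
- Mean event probability: 0.8 × 0.0454 + 0.2 × 0.1008 = 0.0565.
- N = 71.8/0.0565 = about 1,271; divided by 0.85 this is 1,495, against 1,500 stated.

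The Poisson model plays no part in this sizing.

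**Effect of omitting prior doses.** Let pv and pd be the shares with more prior doses among vaccinees and decliners, and R the infection rate ratio of more against fewer doses. With equal follow-up and the same R in both groups, the rate ratio is multiplied by

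B = (pv·R + 1 - pv) / (pd·R + 1 - pd), and apparent VE = 1 - (1 - true VE) × B.

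The documents give none of pv, pd or R, so all three are assumed. True VE is set at 50%.

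| pv / pd | R = 0.7 | R = 1.25 |
|---|---|---|
| 50% / 50% | B = 1, VE 50.0% | B = 1, VE 50.0% |
| 60% / 40% | 0.82/0.88 = 0.932, VE 53.4% | 1.15/1.10 = 1.045, VE 47.7% |
| 70% / 30% | 0.79/0.91 = 0.868, VE 56.6% | 1.175/1.075 = 1.093, VE 45.3% |
| 80% / 20% | 0.76/0.94 = 0.809, VE 59.6% | 1.20/1.05 = 1.143, VE 42.9% |

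The extremes are 42.9 - 50 = -7.1 and 59.6 - 50 = +9.6 points.

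If the ratio of the plan's two rates were taken as the dose effect (48/60, so R = 0.8), the three unbalanced rows would give 52.2%, 54.3% and 56.25%. That ratio describes last season and may not carry over.

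**Simulation check.** Poisson counts were generated for 1,020 vaccinees and 255 decliners (85% of 1,200 and 300), with 24 weeks each and 300 replicates. Models were fitted with and without the dose term, and without a month term.
- 70/30, R = 0.7: VE 56.0% without the term, 49.6% with it.
- 70/30, R = 1.25: 44.7% without, 49.8% with.
- 50/50: 48.4% and 48.5% (R = 0.7), 51.0% and 50.9% (R = 1.25). The term makes no difference here; the distance from 50% is simulation noise.

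**Age group and sex.** Table 1 sets at least 300 of 1,200 and at least 75 of 300 in each of four cells, 25% in both groups. If the goals are met, B = 1 for these factors. Age differences within the two broad bands remain possible.

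**The case against.** The strongest reply is that the plan defines VE through the Cox model (SAP 8.3.1), so a Poisson rate ratio is not VE here. Secondary objective 2, "Assess the vaccine efficacy against asymptomatic or any (asymptomatic or symptomatic) RAT-confirmed SARS-CoV-2 infections", would then be estimated by Cox regression, and the mismatch with the primary VE would not arise. The incidence sentence can also be read as descriptive: it speaks of calculating incidence and mentions no test or rate ratio. The confounder sentence might be meant to cover every model in the section. SAP 7.5 also says that the need to adjust for time since last infection or vaccination will be assessed.

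Much of this stands. A reader might infer that VE against asymptomatic or any infection will come from the month-only model. The documents do not say so; they assign no model to objective 2 by name. A reader might also infer that omitting age and sex biases the comparison. Recruitment goals address age group and sex, and sex is not a fixed term in the primary model either. Nor is the primary model always adjusted: analyses with fewer than 10 events are unadjusted.

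What remains is narrower. SAP 8.1 names Poisson regression for comparing rates, so comparative use is provided for. SAP 7.1 ties its fixed covariates to the primary objectives. The confounder sentence closes a paragraph on other models and lists nothing, and the SAP 7.5 provision leaves adjustment optional and does not name number of prior doses.

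**Conclusion.** The point holds as a limited one. As specified, the Poisson model leaves a comparison of vaccinees with decliners open to confounding by prior doses, and its rate ratios are not adjusted like the primary VE.

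It would go too far to say that the estimates are confounded, or that VE will be inflated. Both need a dose imbalance and a dose effect that the documents do not supply, and the shift can go either way. Under the assumed ranges it is about -7 to +10 points around a true VE of 50%, and zero without imbalance.

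The randomized comparison of NVX with mRNA, the primary VE analysis and the sample size are unaffected.

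**What to change.** In Protocol 6.1.4 and SAP 8.3.2:
- Add age and prior-dose category, coded as in the primary Cox model, to the Poisson model whenever it compares vaccinees with decliners.
- Report adjusted rates and rate ratios beside the crude ones.
- State that VE against asymptomatic or any infection (secondary objective 2) uses the Cox model with the primary covariate set.

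The look-back for prior doses must be settled first, because SAP 7.1 says 3 years while Protocol 6.1.2 and SAP 8.3.1 say 4.

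The cost is a wording change, a little more analysis work and slightly wider intervals against decliners. No new data are needed: age comes from the enrollment survey (Protocol 5.5.1.1), and prior doses from the state registry or participant records (Protocol 5.5.3.2).

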7.1 Data Sharing

Westat, Inc. will deliver Full Data Sets to University of Utah. Westat, Inc. will deliver Limited Data Sets (de-identified) to Novavax, Inc. This is a two-part data delivery component:

- 1. Westat will regularly clean and share identifiable data sets with UT.
- 2. Westat will only share a final, de-identified data set with Novavax.

8. Protection of Human Subjects

8.1 IRB Review

Prior to study implementation, the protocol, informed consent form, participant education and recruitment materials, data collection instruments and other documents associated with the protocol shall be approved by the University of Utah IRB as the IRB of record responsible for overseeing study activities. All protocol amendments must be approved by the IRB prior to implementation. The Investigator/Sponsor or designee (i.e. co-investigator or study coordinator) will be responsible for submitting documents for initial approval, continuing review, amendments, and all unanticipated problems involving risk to human participants or others according to IRB policy. The records of IRB approvals will be maintained in in the regulatory record/file and University of Utah's Electronic Research Integrity & Compliance Administration system (ERICA), as applicable.

An IRB authorization agreement using the Streamlined, Multisite, Accelerated Resources for Trials IRB Reliance platform (SMART) IRB platform will be established for Westat to rely on UT for oversight of study activities involving human subjects and any associated identifiable data. University of Utah will obtain additional approval from the appropriate independent ethics committees or IRBs as required by their institution.

8.2 IRB Reporting Requirements

An incident refers to an unanticipated problem that occurs during the research study. Incidents may or may not involve a risk of harm to study participants. For the BEEHIVE study, examples of incidents include protocol deviations, i.e., anytime established study protocols are not followed; confidentiality breaches; participant complaints; events involving participants' safety and health; and problems related to study procedures such as the consent, enrollment, study vaccine, or test kit administration. Within 24 hours of learning about an incident, study staff will complete the BEEHIVE Incident Report Form (Appendix R1) in the study portal and notify the designated BEEHIVE study coordinator that an incident report form has been completed for a specific participant ID. For all protocol deviations, adverse events, serious adverse events, and participant withdrawals noted in the Incident Report Form, study staff will also be prompted to complete the University of Utah Protocol Deviation Log (Appendix R4), Adverse Event Log (Appendix R2) or Serious Adverse Event Log (Appendix R3). The BEEHIVE study coordinator will review the information received for all incidents and complete all required submissions to the University of Utah IRB.

8.3 Vaccine Products

Two COVID-19 vaccine products will be used in this trial: NVX vaccine (Novavax COVID-19 Vaccine, Adjuvanted, 2023-2024 formula (monovalent, Omicron XBB.1.5 containing)) or mRNA vaccine (Pfizer-BioNTech COVID-19 Vaccine, 2023-2024 formula (monovalent, Omicron XBB.1.5 containing)). Novavax, Inc. will provide the research team with the NVX vaccines for the trial. University of Utah will purchase the Pfizer mRNA vaccines when it is commercially available in Fall 2023.

Information on the individual vaccine products and details on storage and monitoring will be included in the Appendices once the vaccine products are available. Both vaccines have received approval or authorization prior to use in this trial. The Pfizer vaccine has received approval from the FDA for use in persons aged ≥ 12 years in the United States as of September 12, 2023 (Appendix V2. Pfizer COVID-19 Vaccine Fact Sheet). The Novavax vaccine has received Emergency Use Authorization (EUA) from the FDA for use in persons aged ≥ 12 years in the United States as of October 3, 2023 (Appendix V1. Novavax COVID-19 Vaccine Fact Sheet).

The study vaccines will only be administered to participants under the care of the Investigator/Sponsor. The study vaccines will be stored in a locked temperature monitored medication refrigerator at the University of Utah Clinical & Translational Science Institute (CTSI). The study vaccines will be under temperature monitoring continuously. If there is a temperature excursion, the affected study vaccines will be quarantined and status of quarantine will be documented per local policy. We will follow manufacturer storage guidance to determine if the vaccine is still appropriate to be used. If it is not appropriate for use, the affected vaccines will be destroyed or returned to the manufacturer. At the end of the study, unused vaccines will be destroyed per local policy.

